8.3. Subject Withdrawal Criteria

The Investigator or subject themselves may stop study treatment at any time for safety or personal reasons.

Any subject with a CDRS-R assessment indicative of the onset of a new depressive episode at any visit can be discontinued from study participation at the discretion of the Investigator. Any subject with a new positive response on questions 4 and/or 5 of the C-SSRS will be immediately discontinued and evaluated for risk. Dosing may be restarted at the discretion of the Investigator following consultation with the Sponsor or its designee.

Where possible, a subject who discontinues treatment will undergo the protocol-specified end-of study procedures at the time of discontinuation. Date and reason(s) of premature discontinuation will be described on the CRF. In addition, the date of last dose of study treatment will be recorded on the Study Treatment Dosing CRF.

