7.5. Criteria for Subject Study Discontinuation

A subject may elect to discontinue from the study at any time for safety or personal reasons. All subjects who discontinue from the study should complete the early study discontinuation procedures.

Any subject with a new positive response on questions 4 and/or 5 of the C-SSRS will be immediately discontinued and evaluated for risk. Dosing may be restarted at the discretion of the Investigator following consultation with the Sponsor or its designee.

Subjects who discontinue early from the study will be discontinued for one of these primary reasons: AE(s), lost to follow-up, subject choice, inadequate therapeutic effect, and administrative/other. In addition to the primary reason, the subject may have indicated 1 or more of these reasons as secondary reasons for discontinuation. Study disposition information will be collected on the case report form (CRF).

 Table 2:
 Study Design and Schedule of Assessments

Assessment ⁴	Baseline* (Titration)					Tr	eatmo	End of Study / Early Termination	Follow Up Visit	Follow Up Phone Call					
Study Month	0	1	2	3	4	5	6	7	8	9	10	11	12	One and Two Weeks Post Last Dose	30 Days After Last Dose
Study Visit Number	1	2	3	4	5	6	7	8	9	10	11	12	13	14 & 15	
Visit Window		±3 days	±3 days	±3	±3	±3 days	±3 days	±3 days	±3 days	±3 days	±3 days	±3 days	±3 _{days}	±3 _{days}	±3days
Informed Consent	X														
Inclusion/ Exclusion	X														
Medical/Psychiatric/ Medication History	X														
Physical Examination	X	X		X			X			X			X	X	
Vital Signs ¹	X	X	X	X	X	X	X	X	X	X	X	X	X	X	
ECG	X	X		X			X			X			X		
Laboratory Tests (Hematology, Chemistry and Urinalysis) ²	X	X		X			X			X			X	X	
Urine Drug Screen	X	X		X			X			X			X		
Urine Pregnancy Test	X	X		X			X			X			X		
HbA1c		X		X			X			X			X		
YGTSS Score	X	X		X			X			X			X		
CGI-TS-I		X		X			X			X			X		

Confidential Page 34 of 76

Assessment ⁴	Baseline* (Titration)					Tr	eatm	End of Study / Early Termination	Follow Up Visit	Follow Up Phone Call					
Study Month	0	1	2	3	4	5	6	7	8	9	10	11	12	One and Two Weeks Post Last Dose	30 Days After Last Dose
Study Visit Number	1	2	3	4	5	6	7	8	9	10	11	12	13	14 & 15	
CGI-TS-S	X	X		X			X			X			X		
C&A-GTS-QOL	X	X		X			X			X			X		
Columbia Suicide Severity Rating Scale	X	X	X	X	X	X	X	X	X	X	X	X	X	X	
Abnormal Involuntary Movement Scale (AIMS)	X	X	X	X	X	X	X	X	X	X	X	X	X		
Barnes Akathisia Ratings Scale (BARS)	X	X	X	X	X	X	X	X	X	X	X	X	X		

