8.2. Subject Exclusion Criteria

- 1) Subjects with a clinical presentation and/or history consistent with another neurologic condition that may have had accompanying abnormal movements (e.g., Huntington's disease, Parkinson's disease, Wilson's disease, stroke, Restless Legs Syndrome).
- 2) History of schizophrenia, bipolar disorder, or other psychotic disorders.
- 3) Any unstable primary mood disorder (DSM-5 criteria) at time of Baseline.
- 4) Subjects who have unstable medical illness or clinically significant abnormalities on laboratory tests or ECG at Baseline as determined by the Principal Investigator.
- 5) Subjects who have moderate to severe renal insufficiency at Screening.
- 6) Subjects with a major depressive episode in the past 2 years.
- 7) Subjects with a history of attempted suicide.
- 8) A significant risk of committing suicide based on history, routine psychiatric status examination, Investigator's judgment, or who had an answer of "yes" on any question other than 1–3 (currently or within the past 30 days) on the baseline/screening version of the C-SSRS.
- 9) Subjects with a history of seizures (excluding febrile seizures that occurred <2 years prior to Baseline).
- 10) Subjects with a myocardial infarction within 6 months.

- 11) Female subjects who are currently pregnant or lactating or planning to become pregnant during the course of the study.
- 12) Subjects who have a need for medications which would have unfavorable interactions with ecopipam, e.g., dopamine antagonists or agonists [including bupropion], tetrabenazine, monoamine oxidase inhibitors, or St. John's Wort.
- 13) Subjects with current or recent (past 3 months) DSM-5 substance use disorder (with the exception of nicotine).
- 14) Subjects with positive urine drug screen for cocaine, amphetamine, methamphetamine, benzodiazepines, barbiturates, phencyclidine (PCP) or opiates at Baseline, except those receiving stable, prescribed treatment for ADHD. Subjects with urine positive only for benzodiazepines will be exclusionary unless medically prescribed.
- 15) Subjects with a lifetime history of bipolar disorder type I or II, dementia, schizophrenia, or any other psychotic disorder.
- 16) Inability to swallow tablets.
- 17) Subjects with a known hypersensitivity to ecopipam or any of its excipients.
- 18) Any subject who in the opinion of the investigator is not a suitable candidate for the study.

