12. ASSESSMENT OF SAFETY

12.1. Safety Parameters

Study Visits may be completed in locations other than clinic and/or via remote administration due to restrictions as a consequence of the COVID-19 pandemic or other qualifying event. Safety will be monitored throughout the study at all visits by repeated adverse event (AE) monitoring, vital signs, the Columbia-Suicide Severity Rating Scale (C-SSRS), the Abnormal Involuntary Movement Scale (AIMS), the Barnes Akathisia Rating Scale (BARS), the Pediatric Anxiety Rating Scale (PARS) and Children's Depression Rating Scale-Revised (CDRS-R). In addition to these assessments, at Baseline, Months 1, 3, 6, 9 and 12 safety will also be monitored by clinical and laboratory evaluations and electrocardiogram (ECG) monitoring. At the Follow Up visit, AE monitoring, the C-SSRS, clinical and laboratory evaluations and vital signs will be assessed. Laboratory evaluations will include hematology, chemistry, urine values and HbA1c. A Follow Up phone call will be conducted 30 days after the last dose of study medication to assess AEs. Additional assessments (all visits except the follow up visit) will include the AIMS, the BARS, the CDRS-R and the PARS. C-SSRS will also be assessed (all visits including the Follow Up visit).

The C-SSRS is a low burden (approximately 5 minutes for completion) instrument to assess both suicidal behavior and ideation. The scale is appropriate for subjects from age 6 through to an elderly population.

The AIMS records the occurrences of tardive dyskinesia (TD) in subjects receiving neuroleptic medications. The test is used to detect TD and to follow the severity over time.

Barnes Akathisia Rating Scale (BARS) scale to assess the severity of drug-induced akathisia. Objective and subjective items in the scale measure the level of subject's restlessness.

Children's Depression Rating Scale-Revised (CDRS-R) is a clinically validated rating scale designed to assess psychiatric signs and symptoms of depressions in children and adolescents.

Pediatric Anxiety Rating Scale (PARS) is a clinician-rated instrument for assessing the severity of anxiety symptoms associated with common anxiety disorders and generalized anxiety in children and adolescents.

Vital Signs:

Vital signs will be collected each clinic visit. They include heart rate, blood pressure, orthostatic blood pressure and heart rate (after being supine for 5 minutes and 3 minutes after standing), height and weight.

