9.8. Other Safety

9.8.1. Columbia Suicide Severity Rating Scale (C-SSRS)

The C-SSRS is a low burden (approximately 5 minutes for completion) instrument to assess both suicidal behavior and ideation. The scale is appropriate for subjects from age 6 through to an elderly population.

The number and percentage of subjects with suicidal behavior and ideation will be summarized at all visits during the treatment, end of study/early termination and follow up visits.

All questionnaire data will be displayed in a listing.

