	16.2.8.4	Physical Examination	Safety Set
	16.2.8.5.1	Columbia-Suicide Severity Rating Scale (C-SSRS) – Suicidal Ideation	Safety Set
	16.2.8.5.2	Columbia-Suicide Severity Rating Scale (C-SSRS) – Intensity of Ideation	Safety Set
	16.2.8.5.3	Columbia-Suicide Severity Rating Scale (C-SSRS) – Suicidal Behavior	Safety Set
	16.2.8.5.4	Columbia-Suicide Severity Rating Scale (C-SSRS) – Actual Attempts	Safety Set
	16.2.8.6	Abnormal Involuntary Movement Scale (AIMS)	Safety Set
	16.2.8.7	Barnes Akathisia Rating Scale (BARS)	Safety Set
	16.2.8.8	Children's Depression Rating Scale Revised (CDRS-R)	Safety Set
	16.2.8.9	Pediatric Anxiety Rating Scale (PARS)	Safety Set
	16.2.9.1	Height, Weight and BMI Z-Scores	Safety Set

This document is confidential.

16. Index of Figures

Header	Figure Number	Name	Analysis Set (Example)
14.2	14.2.1.4.1a	Mean (+/- SD) C&A-GTS-QOL Change from Baseline Total Score Over Time	miITT Set
	14.2.1.4.1b	Mean (+/- SD) VAS Change from Baseline Score Over Time	miITT Set
14.3	14.3.4.6a	Mean (+/- SD) BMI z-Score Over Time	Safety Set
	14.3.4.6b	Mean (+/- SD) Height z-Score Over Time	Safety Set
	14.3.4.6c	Mean (+/- SD) Weight z-Score Over Time	Safety Set

This document is confidential.

17. Appendices

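### The mandatory suicidality stop is tied only to C-SSRS questions 4 and/or 5, so suicidal behavior or an attempt without a new positive there requires no hold or risk evaluation

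*Protocol*

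**What the plan says.** Protocol Sections 7.5 and 8.3 carry the same rule. In Section 8.3 it reads: "Any subject with a new positive response on questions 4 and/or 5 of the C-SSRS will be immediately discontinued and evaluated for risk". Section 7.5 has the same trigger, a "new positive response on questions 4 and/or 5 of the C-SSRS", and the same consequence: an immediate stop and a risk evaluation. The next sentence governs return to treatment: "Dosing may be restarted at the discretion of the Investigator following consultation with the Sponsor or its designee".

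The other stopping provisions are permissive. Under Section 8.3 the investigator or the subject "may stop study treatment at any time for safety or personal reasons", and a new depressive episode on the CDRS-R can lead to discontinuation if the investigator so decides.

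Suicidal behavior appears elsewhere in the plan:

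- **At entry.** Exclusion 7 in Section 8.2 bars "Subjects with a history of attempted suicide". Exclusion 8 bars a yes on any C-SSRS question beyond the first three, currently or in the past 30 days.
- **In the assessments.** Section 12.1 describes the C-SSRS as an "instrument to assess both suicidal behavior and ideation". It is given at every clinic visit, including the follow-up visits.
- **In the analysis.** SAP Section 9.8.1 states: "The number and percentage of subjects with suicidal behavior and ideation will be summarized at all visits during the treatment". SAP Section 15 has a listing titled "Columbia-Suicide Severity Rating Scale (C-SSRS) – Suicidal Behavior" (16.2.8.5.3) and another for actual attempts (16.2.8.5.4), both separate from the ideation listing (16.2.8.5.1).

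**The concern.** The plan treats a past attempt as a reason to keep a child out, and it collects behavior and attempts during the study. Yet the only sentence that compels action on treatment names two C-SSRS questions and nothing else. A site that follows Sections 7.5 and 8.3 to the letter could keep dosing a child after suicidal behavior on one investigator's judgment, with no required risk evaluation.

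This matters because suicidality is a recognized risk for the drug. Section 5.3.1 reports suicidal ideation in pediatric subjects on ecopipam in both the blinded study and its open-label extension. Section 5.2.2.1 reports that three Phase 3 obesity studies were discontinued for psychiatric adverse events (31% on ecopipam, 15% on placebo) that included suicidal ideation.

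**Working it through.** No arithmetic lies behind the rule, so the check sets the provisions side by side. The rule carries three safeguards: (a) an immediate stop, (b) a risk evaluation, (c) sponsor consultation before restart.

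| On-study situation | (a) Stop | (b) Risk evaluation | (c) Consultation before restart | Required |
|---|---|---|---|---|
| New positive on question 4 and/or 5, with or without behavior | yes | yes | yes | 3 of 3 |
| Behavior or attempt, no new positive on 4 or 5 | optional | not stated | not stated | 0 of 3 |
| As the row above, but also a compliance violation | optional | not stated | joint evaluation under 9.4, no explicit hold | 0 of 3 as written, with a partial substitute for (c) |

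The second and third rows depend on what else in the plan reaches such an event:

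1. **Adverse event recording (Section 12.4).** Action taken must be recorded. No action is prescribed.
2. **Special-interest status (Section 13.2.1; SAP Section 9.3).** The protocol names suicidality, and the SAP names depression with suicide and self-injury. The consequence is tabulation and listing.
3. **Serious adverse event reporting (Sections 12.2.1.2 and 12.5).** An attempt may qualify, including as an important medical event, and is then reported within 1 business day. This depends on a seriousness criterion and has no dosing consequence. Dosing is once each evening (Section 10.5), so a dose can be taken before the report is due.
4. **Investigator stop (Section 8.3).** Permitted, not required.
5. **Compliance evaluation (Section 9.4).** Any compliance violation requires the investigator and sponsor to decide whether the subject may continue. An overdose of study tablets would be one. Section 9.4 covers that route only, and it specifies neither a hold in the meantime nor a suicide-risk evaluation.

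Timing adds to the gap. The trigger is a C-SSRS response, and the scale is scheduled monthly during treatment. An event reported between visits as an adverse event does not itself meet the trigger.

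The entry and on-study wordings also differ in scope. Entry names attempts and takes in every C-SSRS question beyond the first three. The on-study rule names questions 4 and 5 only. No reason is given for the narrower scope.

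**The case against.** The strongest reply is that the uncovered group may be nearly empty. A child who attempts suicide and also newly answers yes to question 4 or 5 is already covered in full. The documents do not print the C-SSRS items, so they cannot show how often behavior would occur without such an answer. This stands, and it limits the point to behavior or an attempt without a new positive. A reader might infer that every on-study attempt escapes the rule, or that the plan ranks behavior below ideation. The documents support neither.

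A second reply is that the event is handled elsewhere. That is true of recording, tabulation and reporting, and Section 9.4 does require sponsor involvement for an overdose of study tablets. It would therefore be wrong to say that nothing happens, or that the sponsor never has to be involved. None of these provisions requires a hold or a suicide-risk evaluation.

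Third, the restart sentence in Section 8.3 follows both the CDRS-R provision and the C-SSRS rule, so it could be read as covering either. In Section 7.5 only the C-SSRS rule precedes it, which favors the narrower reading. Neither reading extends it to suicidal behavior.

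Fourth, harm requires a physician who knows of suicidal behavior and continues dosing. Most would stop. A mandatory rule exists so that this does not rest on one person's judgment, and the sponsor chose such a rule for questions 4 and 5.

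**Conclusion.** The point holds in limited form: the trigger of a stated child-safety rule is too narrow. For suicidal behavior or an attempt without a new positive on question 4 or 5, none of the three safeguards in Sections 7.5 and 8.3 applies, and joint evaluation with the sponsor is required only where Section 9.4 is engaged.

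No event rate is claimed. The number affected is probably small: the available protocol text cites no suicidal behavior on ecopipam, and Section 5.2.2.1 reports no evidence of an effect on the C-SSRS in the earlier pediatric crossover study (PSY302).

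The conclusion rests on behavior not being named in the trigger, and on no provision elsewhere in the available text filling the gap. The emergency-contact page was not available and is not relied on. The textual omission is certain; its practical size is not. It is worth fixing because the correction is cheap and the needed data are already collected.

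**What to change.** In both Section 7.5 and Section 8.3, keep the existing trigger and make three changes:

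- After the reference to questions 4 and/or 5, add: *or with any new suicidal behavior (including any suicide attempt) since the last assessment, whether reported on the C-SSRS or as an AE*.
- State that the sentence on restart after sponsor consultation applies to both triggers.
- State that an event already evaluated and cleared for restart does not trigger the rule again, but a further event does.

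The cost is a few sentences in two sections, site training, and possibly a few more interrupted subjects. No new assessment is needed. The SAP needs no change, because behavior is already summarized and listed.

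SAP Section 10 records updates made after database lock. If dosing in this trial has ended, the change cannot act here and should be carried into later ecopipam protocols that reuse the rule.

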9. TREATMENT OF SUBJECTS

9.1. Description of Study Drug

Table 3: Investigational Product

	Investigational Product	
Product Name:	Ecopipam	
Active Pharmaceutical Ingredient:	Ecopipam hydrochloride	
Dosage Form:	Tablets	
Unit Dose (expressed as the free base)	12.5-, 37.5-, 50-, 75-, and 100 mg	
Route of Administration	Oral	
Physical Description	Round, biconvex, light blue film-coated tablet, plain on both sides	
Manufacturer	Corealis Pharma, Inc.	

9.2. Concomitant Medications

For subjects who receive study treatment, any medication (including over-the-counter medications) administered to the subject during the course of the study (starting at the date of informed consent) will be recorded on the Prior and Concomitant Medication CRF. Nonpharmacologic therapies/procedures will also be captured on the CRF. Non-dopaminergic blocking tic treatment could be allowed in consultation with the PI. The Investigator will record any AE on the Adverse Events CRF for which a concomitant medication was administered.

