6.2. Secondary Objectives

The secondary objective of this study is to evaluate the durability of effect of ecopipam in pediatric subjects (aged ≥ 6 to ≤ 18 years at Baseline) with TS.

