9.3. Prohibited Therapies

Since ecopipam and its metabolite (SCH40853) may inhibit CYP2D6, OATP1B1, PGP and UGT1A9, for any drug that is a substrate of these enzymes, the label for the drug should be consulted to decide if a dose adjustment is needed. Drugs that are strong inducers of these enzymes are prohibited. An illustrative list of such drugs is provided in the Prohibited Medications List in the Appendices.

Prohibited therapies per the exclusion criteria (Section 8.2) include medications which would have unfavorable interactions with ecopipam:

• Dopamine antagonists or agonists (including bupropion)

- Tetrabenazine
- Monoamine oxidase inhibitors
- St. John's Wort

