- Intrauterine hormone-releasing system (IUS)
- Bilateral tubal occlusion
- Vasectomized male partner
 - Vasectomized partner is a highly effective birth control method provided that
 partner is the sole sexual partner of the woman of childbearing potential study
 participant and that the vasectomized partner has received medical assessment of
 the surgical success.
- Sexual abstinence (defined as refraining from heterosexual intercourse during the entire period of exposure associated with the study treatment).
 - In the context of this guidance, sexual abstinence is considered a highly effective method only if defined as refraining from heterosexual intercourse during the entire period of risk associated with the study treatments. The reliability of sexual abstinence needs to be evaluated in relation to the duration of the clinical study and the preferred and usual lifestyle of the subject.

Adapted from: Clinical Trials Facilitation Group (CTFG). Recommendations Related to Contraception and Pregnancy Testing in Clinical Trials. September 15, 2014.

Available at: https://www.hma.eu/fileadmin/dateien/Human_Medicines/01-About_HMA/Working_Groups/CTFG/2014_09_HMA_CTFG_Contraception.pdf

PROHIBITED MEDICATIONS LIST

Examples below are not exclusive.

- Any new stimulant for the treatment of ADHD that the subject was not taking at Baseline is also prohibited.
- Other medications used to treat TS are prohibited.
- Dopamine depleting medications are prohibited.
- D2 receptor antagonists are prohibited.

Prohibited Antipsychotic Medications		
Aripiprazole	Loxapine	
Cisapride	Methylphenidate	
Clonidine	Paliperidone	
Dextroamphetamine	Pimozide	
Dronedarone	Risperidone	
Droperidol	Thioridazine	
Fluoxetine	Topiramate	
Guanfacine	Ziprasidone	
Haloperidol		

Other Prohibited Medications for the Treatment of Tics	Mechanism
Any dopamine agonist (e.g., ropinire	ole, pramipexole)
Baclofen	GABA-B receptor agonist
Clonazepam	GABA-A receptor positive allosteric modulation
Duetetrabenazine	VMAT2 inhibitor / monoamine depleter
Guanfacine	Alpha-2A adrenergic receptor agonist
Reserpine	VMAT1/2 inhibitor / inhibits uptake of dopamine
Tetrabenazine	VMAT2 inhibitor / monoamine depleter
Valbenazine	VMAT2 inhibitor / monoamine depleter

Other Prohibited Medications	Mechanism
Chloroethylnorapomorphine	D2 receptor antagonist
Chlorpromazine	D2 receptor antagonist/ antipsychotic
Cinnarizine	Antihistamine/ calcium channel blocker/ Interaction with D2 receptors

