5.3. Modified Intent-to-Treat Set

The Modified Intention-to-Treat (mITT) set will consist of all subjects who receive at least one dose of study drug and have at least one post Baseline scoring of YGTSS. All efficacy analyses will be conducted using the mITT population.

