8.1. Yale Global Tic Severity Scale (YGTSS)

The YGTSS is a clinician-completed rating scale used to quantify overall tic severity as well as specific subdomains of tic number, frequency, intensity, complexity and interference. Each of these subdomains is scored, on a 5-point scale, separately for motor and vocal tics and then summed across both motor and vocal tics to yield a total tic score (TTS) ranging from 0 to 50. The YGTSS also provides for an overall impairment rating (0 = “none” to 50 = “severe”). Global YGTSS (YGTSS-GS) is the total of YGTSS-TTS and impairment score (YGTSS-I). Efficacy will be analyzed for the YGTSS-TTS, YGTSS-I and YGTSS-GS.

The observed YGTSS-TTS along with motor and phonic subdomains, YGTSS-I and YGTSS-GS values and their changes from baseline will be summarized by visit. The paired t-test will be used for analyzing the change from baseline within treatment.

The percent of subjects with a 25% or greater improvement on the YGTSS-TTS score at any time between the Baseline visit and post-baseline visit will be considered as a Response. Any subject who has at least 1 Response (>=25% improvement) will be considered as a Responder; otherwise, the subject will be considered a Non-Responder. Responder and Non-Responder will be summarized at each post-baseline visit and overall.

YGTSS-TTS will also be summarized by treatment group (ecopipam, placebo and overall) from CL (EBS-101-CL-001) study.

All YGTSS data will be presented in a listing.

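### Protocol 9.2 and the Prohibited Medications List disagree on tic drugs that do not block dopamine, and the SAP does not link a newly started tic drug to the durability results; the size is unknown and may be small

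*Protocol*

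**What the plan says.** **Protocol, which drugs are allowed.** Section 9.2 (Concomitant Medications) states: "Non-dopaminergic blocking tic treatment could be allowed in consultation with the PI". The Prohibited Medications List in the appendix states: "Other medications used to treat TS are prohibited". Its table headed "Other Prohibited Medications for the Treatment of Tics" includes guanfacine, baclofen and clonazepam and gives them adrenergic or GABA mechanisms. Section 9.3 points to the list with these words: "An illustrative list of such drugs is provided in the Prohibited Medications List in the Appendices". That sentence follows text on enzyme substrates and inducers. The bullets in 9.3 name dopamine antagonists and agonists, tetrabenazine, monoamine oxidase inhibitors and St. John's Wort, but none of the three drugs above.

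**Protocol, objective.** Section 6.2: "The secondary objective of this study is to evaluate the durability of effect of ecopipam in pediatric subjects".

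**SAP, medication data.** Section 7.4 plans prior and concomitant tables in the Safety Set and a by-subject listing (Tables 14.1.4.1 and 14.1.4.2, Listing 16.2.4.4). Section 6.3 imputes partial medication dates only to set prior or concomitant status.

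**SAP, efficacy.** Section 5.3: "All efficacy analyses will be conducted using the mITT population". Section 5.4 repeats them in all enrolled subjects. Section 8 summarizes change from baseline by visit with paired t-tests. For YGTSS-TTS it adds: "Any subject who has at least 1 Response (>=25% improvement) will be considered as a Responder", and "Responder and Non-Responder will be summarized at each post-baseline visit and overall". None of these rules mentions other tic treatment.

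**The concern.** Durability is judged from uncontrolled change within subjects. If tics return during the year, adding another tic drug is a natural response. The later score then reflects both drugs, but the tables would show it as the effect of continued ecopipam. A subject with no earlier Response could also become a Responder on the strength of a single visit after the new drug.

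The protocol conflict adds a second problem. One site can record a guanfacine start as permitted under 9.2, and another can record it as a deviation under the appendix. The deviation table is therefore not a reliable count of such starts.

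**Working it through.** **1. Do the two protocol texts conflict?** Section 9.2 opens the door, through the principal investigator, to tic treatment that does not block dopamine. The appendix closes it for other Tourette's medication and names three drugs of that kind. The appendix does qualify another ban, since new ADHD stimulants are barred only if the subject was not on them at Baseline. The ban on Tourette's medication has no such qualifier. No text says which rule prevails.

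The sentence before the permission in 9.2 concerns non-drug therapy, so the permission could be read that way. This is unlikely, because the section is about medications and the wording describes a drug mechanism.

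**2. Where does an added tic drug go in the SAP?** It goes into the concomitant table and the medication listing. If a site codes it as a deviation, it also goes into Table 14.1.2.1 and Listing 16.2.2.1. The path ends there. There is no per-protocol set, and Sections 5, 6 and 8 contain no flag, censoring rule or sensitivity analysis for it. Scores after the start therefore count by silence. Stable use since before Baseline largely cancels in a change score, so the issue is new starts.

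**3. How far can the overall Responder percentage move?** The plan gives no figure to reproduce. Let N be the subjects in Table 14.2.1.1.5 and q the share of them who started a tic drug after first dose. Compare the planned count with one in which scores after the start cannot create a Response, using the same N.

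- A subject's status differs only if three things hold: a tic drug was started, no Response came before the start, and at least one came after it.
- The number of such subjects is at most the number of starters, qN.
- Difference in percentage ≤ qN / N = q.

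The documents do not give q. Purely as assumed values, q = 2% caps the rise at 2 percentage points and q = 20% caps it at 20. The true rise is smaller to the extent that starters had already responded or never respond.

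**4. Can q be read from the planned medication tables?** For one drug, let c be users continuing from before first dose, n new users and s users who stopped before first dose.

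- With complete dates: concomitant = c + n and prior = c + s, so concomitant − prior = n − s ≤ n. This looks like a lower bound on new users.
- SAP 6.3 breaks it. When the known part of a partial start date matches the first-dose month or year, and the default date falls before first dose, the start is set to the first-dose date. Suppose this happens to m continuing users. They leave the prior table and stay in the concomitant one, so the difference becomes n + m − s, which can exceed n.
- Example: three continuing users with year-only start dates in the first-dose year, none new and none stopped. The difference is 3 − 0 = 3, and the true number of new users is 0.

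The tables therefore neither give nor bound the number of starters.

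**5. Mean scores.** At a visit, shift in mean = (share of scores that follow a new drug) × (average extra effect of that drug). The documents supply neither factor.

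**The case against.** The case for leaving the plan alone has several parts.

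- Using every observed score, whatever else the subject takes, is a legitimate treatment-policy approach. This stands, and the all-scores analysis should remain the main one. What is missing is a statement that it was chosen.
- Efficacy is secondary, single-arm and largely descriptive, and tics wax and wane anyway. This also stands and limits the weight of the point.
- Protocol 7.5 lists inadequate therapeutic effect as a reason to discontinue, so some subjects may leave rather than add a drug. This is plausible and could make q small.
- Section 9.2 may be meant as a case-by-case exception to the list. It may be, but neither text says so.

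Three stronger readings are tempting, and the documents do not support them.

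- *The affected results are hidden.* They are not. Listing 16.2.4.4 can be matched by subject to the YGTSS, CGI-TS and C&A-GTS-QOL listings (16.2.6.1 to 16.2.6.3). What is absent is a summary count.
- *The bias can be put in YGTSS points using PSY302.* That study's Day 30 figures describe ecopipam: a fall of 5.6 points against 3.4 on placebo, with an adjusted difference of 2.1 (95% CI −5.5 to 1.2). They say nothing about the effect of guanfacine, baclofen or clonazepam added to ecopipam, or about how often that happened.
- *A non-responder analysis should replace or lead the planned one.* That is a preference, and harder to defend when introduced after database lock.

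**Conclusion.** The point holds as a minor one. The protocol gives two rules for the same drugs, and the SAP lets scores after a newly started tic drug count toward durability without saying that this is intended.

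The size is unknown and may be small. The only assumption-free statement is that the overall Responder percentage is raised by at most the share of subjects who started a tic drug after first dose. A reader might infer that the durability results are materially inflated. The documents give no rate of new starts and no effect for the added drugs, so that inference is not supported. The primary safety objective is little affected.

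**What to change.** **Protocol.** State one rule in Section 9.2 and in the appendix. If conduct is complete, state in the SAP which rule was used to code deviations.

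**SAP Section 8.**

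1. Name the drugs counted as tic medication, fixed before scores are re-tabulated. Start from the appendix tic table and decide on clonidine and topiramate, which the appendix files under antipsychotics.
2. Add a partial-date rule for new versus Baseline use. For example, a drug already in the Baseline medication history is Baseline use, and any other partial date that could fall after first dose counts as new from the earliest such date. Report how many subjects depend on this rule.
3. Report the number of subjects who started a listed drug after first dose.
4. Keep the all-scores analysis as the main one and say so.
5. Add beside it a sensitivity analysis labelled post hoc. In Table 14.2.1.1.5, with unchanged denominators, count starters as non-responders at visits on or after the start date. Overall Responder status stands if a Response came before the start.
6. A summary without post-start scores may be added, but not alone. Dropping those scores can remove subjects who are doing badly and so flatter the mean.

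**Cost.** A wording change, a short drug list that needs clinical judgement, one date rule and one extra set of tables. The medication records are already collected, and SAP Section 10 already accepts additions after database lock, including the Responder table itself. Dose increases of Baseline tic drugs and new non-drug therapy would still not be captured.
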